5.16 Survival Status at Day 28 (+3 day) Visit

Please note that survival status must reflect subject status on or after the 29th calendar day, which is 28 days after the administration of the first dose of the study drug. If subject has died, additional information required includes:

- Date of Death
- Cause of Death (including Death Certificate and autopsy results if available)

5.17 3 Month, 6 Month and 12 Month Follow-Up Visits

Subjects will be contacted to obtain their survival status at 3 months (90 ± 3 Days), 6 months (180 ± 3 Days) and 12 months (360 ± 3 days) post the first dose of study drug. This information can be obtained via telephone or in person. All reasonable efforts must be made to obtain the actual survival status for the subject. At a minimum, there must be 2 documented telephone calls to the subject's last known telephone number and a certified letter sent to their last known address. If a subject cannot be located at 3 months, the same attempts must be made at 6 months and 12 months respectively. Subjects will only be considered lost to follow up if they cannot be located at 12 months post study completion.

5.18 Follow-Up Visits for Subjects who have an anti-ART-123 antibody

Any subject with positive anti-ART-123 antibody results will return to the site at 3 month intervals for collection of a blood sample to be used for determination of presence or absence

of the antibody. Serum samples from subjects that have demonstrated the development of antidrug antibodies that are present on Day 28 or at the “End of Study” Visit will be tested for the presence of neutralizing antibodies.

This process will be continued every 3 months until antibody results are negative or until the subject’s 18 month Follow-Up Visit. Sites will be informed when subjects are antibody positive.

SAEs/thrombotic events information in these antibody positive subjects will be collected and reported to the sponsor over a maximum of 18 months or subject becoming antibody negative, whichever is earlier.

5.19 Schedule of Activities

Table 1: Visit Schedule and Assessments

Assessment Period	Screen-ing	Base-line	Dosing							Post Treatment Follow-up							Long Term FU		
	V1	V2	V3	V4	V5	V6	V7	V8	V9	V10	ETT/ LD24	V11	V12	V13	HD	V14	FU 3m	FU 6m	FU 12m
Study Day		0	1 ³	2 ³	Day 3 Pre	Day 3 Post ³	4 ³	5 ³	6 ³	7 ⁶	ETT Last Dose 24 ± 2 hrs ^b	8-13 ^{1, 9}	14 (+3d) ¹	15-27 ⁹	Hospit-al Discharge (HD) ^{1,2}	28 (+3d)/ EOS ^{a,8}	3 m (90±3 d)	6 m (180±3 d)	12 m (360±3 d)
Informed Consent	X																		
Inclusion/Exclusion Criteria	X																		
Pregnancy Test (serum/urine)	X																		
Platelet, WBC w/ diff and INR (LOCAL laboratory draw)	X																		
Verification of Eligibility (CCC)		X																	
Randomization		X																	
Demographics, Height/Weight		X																	
Medical History and APACHE II		X																	
Vital Signs (Pulse, BP, Respirations, Temperature)		X	X	X		X	X	X	X	X	X		X		X				
Record Con. Med. /Blood Product Admin.		X	X	X		X	X	X	X	X	X	X	X	X	X				
Treatment Given for Current Episode of Sepsis		X																	
Documentation of Infection		X																	
Physical Examination		X																	
12 Lead Central ECG ⁹		X				X	Q ⁵	Q ⁵	X ⁵	X ⁵	X ⁵	Q ⁵	X ⁵		X ⁵				
Assessment of AE/SAE		X	X	X		X	X	X	X	X	X	X	X	X	X	X	X ¹⁰	X ¹⁰	X ¹⁰
ICU Stay and Hospitalization Assessments		X	X	X		X	X	X	X	X	X	X	X	X	X				

Assessment Period	Screen-ing	Base-line	Dosing							Post Treatment Follow-up							Long Term FU		
VISIT	V1	V2	V3	V4	V5	V6	V7	V8	V9	V10	ETT/ LD24	V11	V12	V13	HD	V14	FU 3m	FU 6m	FU 12m
Study Day		0	1 ³	2 ³	Day 3 Pre	Day 3 Post ³	4 ³	5 ³	6 ³	7 ⁶	ETT Last Dose 24 ± 2 hrs ^b	8-13 ^{1, 9}	14 (+3d) ¹	15-27 ⁹	Hospit-al Discha-rge date ^{1,2}	28 (+3d)/ EOS ^{a,8}	3 m (90±3 d)	6 m (180±3 d)	12 m (360±3 d)
Organ Dysfunction Assessments (Shock, Ventilator, Dialysis)		X	X	X		X	X	X	X	X	X	X	X	X	X	X			
LOCAL LABORATORY:																			
Organ Dysfunction Assessments, total bilirubin & serum creatinine		X																	
Organ Dysfunction Assessments, PaO2/FiO2 if vented (use SOC laboratory, if available)		X	X ⁷	X		X	X	X	X	X	X	X	X	X	X	X			
CBC w/differential, Platelets, Coagulation (PT/INR)		X		X		X	X		X	X	X		X		X	X			
CENTRAL LABORATORY																			
Serum Chemistry		X		X		X	X		X	X	X		X		X	X			
D-dimer		X		X		X	X		X	X	X		X		X				
Plasma PK, Exploratory Labs		X			X ⁴	X			X	X	X		X		X				
Arterial lactate		X								X	X								
Anti-ART-123 Antibodies		X											X		X ¹⁰	X ¹⁰	X ¹⁰	X ¹⁰	
Interventions / Surgeries		X	X	X		X	X	X	X	X	X	X	X	X	X	X			
Major Bleeding Events		X	X	X		X	X	X	X	X	X	X	X	X	X	X			
Assessment of the degree of burden and risk threshold, and assess continuation of treatment with ART-123/placebo			X	X		X	X	X	X										
Dispense ART-123/Placebo ²			X	X		X	X	X	X										
Survival Status															X	X	X	X	

Table Footnotes:

- a EOS = End of Study – When a subject is discontinued from the study prior to Day 28 for any reason other than Death (i.e., withdrawal of consent as defined in **Section 2.7.2**). This does not include the subjects who discontinue study drug early, but remain in the study for all other assessments.
- b This visit is performed when a subject is discharged from the hospital on Study Days 1-6 or when a subject remains hospitalized and discontinues study drug administration prior to the 6th dose. The Early Treatment Termination Visit is performed 24 hours (± 2 hours) after the last dose of study medication if study drug administration was discontinued early or this window does not apply. This visit is done in place of the daily study visit.
 1. If the subject is to be discharged from the hospital on Day 13 perform the Day 14 visit in place of Day 13 visit (Hospital Discharge visit is not performed). ONLY if subject has been discharged from the hospital is there a +3 day window for the subject to return for the Day 14 assessments and labs. Subjects who remain hospitalized for Day 14 must have the assessments performed on the 14th calendar day.
 2. **The first dose of study drug must be administered as soon as possible after randomization and within 4 hours. For post-surgical patients that had potentially hemorrhagic surgery the first dose of study drug must not be administered within 12 hours of major surgery.** (See Section 2.6.3.) **All dosing times are based on the first dose of drug. The windows are: Day 2: 24 hours (± 2 hours), Day 3: 48 hours (± 2 hours), Day 4: 72 (± 2 hours), Day 5: 96 hours (± 2 hours) and Day 6: 120 hours (± 2 hours). If IP is held due to surgery refer to Section 3.** Dosing is discontinued when a subject is discharged from the hospital. Administration of study drug is contraindicated if the co-administration of excluded concomitant medication (e.g. full heparinization, oral anticoagulant, anti-platelets drug) is required for subject treatment, or has an intolerable adverse event, such as bleeding events or conditions that place the subject at high risk of bleeding.
 3. Assessments are made within one hour after IP administration on Dosing Days. If blood samples (central, local and Arterial Blood Gas if vented, and not performed as SOC) and ECG are required these are to be completed within (1) hour AFTER study drug administration.
 4. **Within one (1) hour PRIOR to study drug administration, blood samples will be collected.**
 5. **“Q” ECGs** If the QTcB is > 500 msec or the QTcB is > 60 msec over the baseline value, the Investigator should evaluate the subject prior to hospital discharge. If the subject remains hospitalized, continue to monitor ECGs once daily until the earlier of Day 14 or the time when such conditions are no longer met. Use the QTcB from the ECG printout obtained during the study visit for these assessments.
 6. On Day 7, assessments will begin 144 hours (± 2 hours) after the first dose (dosing Day 1) of study drug was administered. If the subject is discharged on Day 7, complete the Day 7 visit (not Hospital Discharge Visit).
 7. **On Day 1 record Arterial Blood Gas only if performed within one hour after IP administration.**
 8. The End of Study Visit occurs whenever the subject discontinues study participation (as defined in **Section 2.7.2**) prior to Day 28. ONLY if subject has been discharged is there a +3 day window for the subject to return to the hospital for Day 28 assessments and labs. Subjects who remain hospitalized on Day 28 must have the assessments performed on the 28th calendar day. (Day 1 is the day of administration of the first dose of study drug.) Survival Status is to reflect survival status on Day 29. If a subject is unable or unwilling to return to the hospital for this visit, information may be collected via telephone. Any required assessments that cannot be done will be recorded as protocol deviations (i.e., laboratory draws).
 9. Beginning with Day 8 all prospective visits are based on calendar days. On study days 8-13 and 15-27, assessments are completed as long as the subject remains in the hospital.
 10. Only subjects that develop anti-drug antibodies to ART-123 will be followed for blood draw and medical evaluation at 3 months intervals until their serum antibody titer results become negative for a maximum duration of 18 months. Subjects who return for testing will be queried for occurrence of any SAEs and clinical evidence of thrombosis.
 11. 3 Month, 6 Month and 12 Month Follow up: Subjects will be contacted to obtain their survival status at 3 months (90 ± 3 Days), 6 months (180 ± 3 Days) and 12 months (360 ± 3 days). If a subject cannot be located at 3 months, the same attempts must be made at 6 months and 12 months respectively. Subjects will only be considered lost to follow up if they cannot be located at 12 months post study completion.
 12. Hospital Discharge (HD) visit applies only to subjects who are discharged from the hospital on Study Day 8 onwards (except for subjects who are discharged on Days 13/14 or Day 28).

6 EFFICACY ASSESSMENTS

Primary Efficacy Endpoint:

- 28 day all-cause mortality

Secondary Efficacy Endpoints:

- Follow-up of all-cause mortality at 3 months
- Resolution of organ dysfunction through Day 28 as measured by:
 - Shock free and alive days
 - Ventilator free and alive days
 - Dialysis free and alive days

Tertiary Efficacy Endpoints:

- Follow-up of all-cause mortality at 6 and 12 months
- Organ Dysfunction (Hepatic, Renal, Respiratory and Cardiac (Septic Shock) at Baseline, Day 3, Day 7, Day 14 and Day 28; Hepatic Dysfunction and Renal Dysfunction will be assessed with central laboratory data (total bilirubin and serum creatinine, respectively)
- ICU free and alive days through Day 28
- Hospitalization free and alive days through Day 28
- INR at Baseline, Day 3, Day 7, Day 14 and Day 28

7 SAFETY ASSESSMENTS AND REPORTING

7.1 Adverse Events

An Adverse Event (AE) is defined as any untoward medical occurrence in a subject administered a pharmaceutical product that does not necessarily have a causal relationship with this treatment. An AE can therefore be any unfavorable and unintended sign, symptom, or disease temporally associated with the use of a medicinal (investigational) product, whether or not considered related to the medicinal (investigational) product. A baseline event refers to medical history that is present prior to the last inclusion criteria being met and obtaining informed consent. Examples of adverse events include:

- Increase in severity of a baseline event

- Clinically significant worsening of laboratory values post baseline (consolidate to a diagnosis if available)
- A new event with an onset date post baseline
- An event present at baseline where more aggressive treatment or an intervention/surgery is required post baseline (e.g. increase in total dosage per day, an invasive intervention such as chest tube insertion, debridement, etc.).

All local and systemic adverse events, whether volunteered by the subject, discovered by Investigator questioning, or detected through other means, will be collected and recorded on the Adverse Event form and followed as appropriate.

Once the patient is authorized to randomize SAEs will be collected through Day 28. Once randomization has occurred both AEs and SAEs are collected. The DAIDS Toxicity/Adverse Event Grading Table ([Appendix I](#)) will be used by the Investigators to grade the events in the Case Report Form. If [Appendix I](#) does not provide severity guidelines for certain events, please see **Section 7.1.1** of the protocol.

AEs will be coded using the Medical Dictionary for Regulatory Activities (MedDRA) terminology by the data management group.

Medical conditions/diseases present before authorization to randomize are only considered AEs if they subsequently worsen in severity, require more aggressive treatment/intervention/surgery, or if they resolve then re-emerge. Whenever possible, a diagnosis will be used to describe the AE. If a diagnosis is not available, the event will be captured using signs and symptoms. Each sign or symptom is its own AE until a diagnosis that they can be collapsed under is known.

Clinically significant laboratory abnormalities (both from central or local laboratories), if not part of a diagnosis, are required to be captured as AEs.

As far as possible, each AE will also be described by:

- The duration (start and end dates)
- The severity grade (Grade 1/mild, Grade 2/moderate, Grade 3/severe, Grade 4/Potentially life threatening as defined by the DAIDS Toxicity Table)
- The relationship to the study drug (none, unlikely, related)
- Whether the AE involved bleeding of any kind
- The action(s) taken
- The outcome

Major Bleeding Events

A Major Bleeding event is defined as:

- any intracranial hemorrhage,
- any life-threatening bleeding,
- any bleeding event classified as serious by the Investigator (e.g., resulting in permanent morbidity),
- the administration of at least 1440 mL (typically 6 units) of packed red cells over two consecutive days.⁶

Note: Should a major bleeding event occur, study product must be discontinued.

All major bleeding events must be collected, documented, and promptly reported as SAEs.

Blood product administration will be recorded in the eCRF.

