7.5 Assessment of Risk Burden

In acknowledgement of the need to provide added oversight for vulnerable populations, monitoring for the degree of burden and risk, and assessment of the appropriateness of continuation of treatment with ART-123/placebo during the dosing period of Days 1-6 will be performed. Since the sepsis subjects enrolled to this study have critically ill conditions at the entry, definitive thresholds based on laboratory assessments or physical examination cannot be defined, and the risk and burden for a subject should be monitored by referring to all the assessments and examinations required for this protocol as well as performed as a standard of care. Additionally, because of the inherent risk of bleeding with compounds such as ART-123, in addition to the assessments called for in the protocol (**Sections 5.6 - 5.10**) study drug must be discontinued in instances where a major bleeding event

(defined in **Section 7.1**) is observed. Additional conditions where study drug must be discontinued are detailed in protocol **Section 2.7.1**.

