10.6.4 Major Bleeding Events

The number of subjects with major bleeds, as defined in [Appendix B](#), will be compared between treatment arms, as will the numbers of subjects with serious major bleeding events. The number of major bleeding events will be compared between groups at Days 3, 7, 14 and overall.

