15.2 Appendix B: Key Study Definitions

Major Bleeding Events

A Major Bleeding event is defined as any intracranial hemorrhage, any life-threatening bleeding, any bleeding event classified as serious by the Investigator (e.g., resulting in permanent morbidity), or any bleeding that required the administration of at least 1440 mL (typically 6 units) of packed red cells over two consecutive days.⁶

All major bleeding events must be collected, documented, and promptly reported as SAEs.

Appropriateness of Initial Antibiotic Therapy

The Investigator will review all culture data from the time of infection onset to determine whether there is a definite identification of a causal organism (i.e., culture from a normally sterile site such as blood or pleural fluid), a likely identification of a causal organism (i.e., culture of suspected pathogen from another site with additional support [e.g., sputum culture where the sputum had < 10 epithelial cells and > 25 WBC per field]), or no causative organism identified. The Investigator will also review initial antibiotic therapy and organism MIC data, to determine whether it was appropriate for the known or suspected causative organism. Such review may include calculations of AUC/MIC relationships based on doses and anticipated clearances.

Mechanical Ventilation

Mechanical ventilation is described for the purposes of this protocol as any kind of ventilation administered via an endotracheal tube or nasotracheal intubation. This applies to all modes of ventilation (VA, VC and PC). Pressure Support Ventilation (PSV) is permissible. Simple administration of supplemental oxygen is NOT considered to be mechanical ventilation.

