##### **Primary Safety Endpoints:**

- Serious Adverse Events
- Major Bleeding Events
- Adverse Events

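### Major bleeding, a primary safety endpoint, has two non-identical definitions: Protocol 7.1, used for reporting and stopping drug, omits the bleeding condition that Appendix B, named for the analysis, attaches to large transfusions

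*Protocol*

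**What the plan says.** Major bleeding is a primary safety endpoint in the protocol synopsis and in SAP Section 3.2. The protocol defines it twice, both times in current text.

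- **Protocol 7.1** gives four bullets. The first three each name hemorrhage or bleeding: intracranial, life-threatening, or judged serious by the investigator. The fourth reads, in full, "the administration of at least 1440 mL (typically 6 units) of packed red cells over two consecutive days". A note below the list makes discontinuation of study product mandatory after a major bleeding event.
- **Protocol Appendix B (15.2)** has the same first three limbs. Its fourth is "any bleeding that required the administration of at least 1440 mL (typically 6 units) of packed red cells over two consecutive days".

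Different parts of the plan point to different versions.

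- Withdrawal from study drug (2.7.1) and SAE reporting (7.2) cite Section 7.1.
- Section 7.5, which says "study drug must be discontinued in instances where a major bleeding event" is observed, also cites Section 7.1 for the definition.
- The statistical section, 10.6.4, begins "The number of subjects with major bleeds, as defined in" and then names Appendix B.
- SAP 4.4.6 plans the tabulation, with exact confidence intervals and a risk difference. It neither defines major bleeding nor cites either protocol definition.

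**The concern.** Read literally, 7.1 makes a large red-cell transfusion a major bleeding event whatever its reason, for example anaemia or haemodilution. The site would report it as an SAE and discontinue study drug. The definition named for the analysis would not count it.

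Two things are at stake.

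1. **Conduct.** Up to 350 centres may read the fourth bullet of 7.1 differently, and that reading determines both SAE reports and exposure to study drug. SAEs are themselves a primary safety endpoint and are reviewed unblinded by the DMC, so transfusion-only reports would enter there too.
2. **Analysis.** SAP 3.7 rules out testing of safety endpoints and plans confidence intervals for major bleeding only. The SAP does not say whether the events tabulated are those the sites report or those that meet Appendix B. If they are the site reports, events that are not bleeding enter both arms of the main bleeding comparison for a drug that acts on coagulation.

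**Working it through.** **Text comparison.** The plan states no figure to reproduce, so the first step sets the two definitions side by side.

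| Element | Protocol 7.1 | Appendix B |
|---|---|---|
| First three limbs | Bleeding named in each | Same |
| Volume in fourth limb | At least 1440 mL packed red cells | Same |
| Period | Two consecutive days | Same |
| Reference cited | 6 | 6 |
| Bleeding condition in fourth limb | None stated | Bleeding must have required the transfusion |
| Cited by | 2.7.1, 7.2, 7.5 | 10.6.4 |

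The bleeding condition is the only substantive difference. Every event that meets Appendix B also meets 7.1; the converse fails for a qualifying transfusion without bleeding. The count under 7.1 is therefore equal to or larger than the count under Appendix B, and no Appendix B event is lost by reporting under 7.1.

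**Illustration of size.** The documents give no rate of major bleeding and none of large transfusion without bleeding, so these inputs are assumptions:

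- n = 400 per arm (800 randomised 1:1, all taken as dosed);
- true major bleeding 5% on ART-123 and 3% on placebo;
- k = 1, 2 or 3 percentage points of transfusion-only events added to each arm;
- site-reported 7.1 events tabulated without filtering.

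SAP 4.4.6 reports a risk difference. With p1 = 0.05 + k/100 and p2 = 0.03 + k/100, the difference is p1 − p2 and SE = √{[p1(1 − p1) + p2(1 − p2)]/400}. This Wald form stands in for the SAP's exact method.

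| k | Rates | Difference | p1(1 − p1) + p2(1 − p2) | SE (points) |
|---|---|---|---|---|
| 0 | 5% vs 3% | 2 points | 0.0475 + 0.0291 = 0.0766 | 1.38 |
| 1 | 6% vs 4% | 2 points | 0.0564 + 0.0384 = 0.0948 | 1.54 |
| 2 | 7% vs 5% | 2 points | 0.0651 + 0.0475 = 0.1126 | 1.68 |
| 3 | 8% vs 6% | 2 points | 0.0736 + 0.0564 = 0.1300 | 1.80 |

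The estimated difference does not move. The standard error grows by about 11% (1.54/1.38) to 30% (1.80/1.38). The approximate 95% half-width, 1.96 × SE, goes from 2.7 points to between 3.0 and 3.5.

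**The case against.** Four arguments can be made on the other side.

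1. **The bullet is shorthand.** It sits under a heading about major bleeding, completes a sentence defining a major bleeding event, and follows three limbs that name bleeding. It also shares its volume, period and reference with Appendix B. This is a natural reading, and 7.1 nowhere says that a transfusion without bleeding counts; it is silent. But the other three bullets state bleeding expressly and this one does not, so the literal reading is also open to a site.
2. **Section 10.6.4 already fixes the analysis definition.** In the protocol it does. A reader might infer that the bleeding comparison will be diluted, but that follows only if site-reported events are tabulated unfiltered. The documents do not say that they will be. Nor do they say that they will not: SAP 4.4.6 names no definition, and no rule states how a transfusion-only report is handled. The argument also leaves reporting and discontinuation unsettled.
3. **The effect measure is a difference.** A reader might infer an attenuated relative risk, from 5/3 = 1.67 to 8/6 = 1.33 on the assumed figures. The SAP plans a risk difference, which equal additions leave unchanged. Only the loss of precision stands, and its inputs are not in the documents.
4. **Few cases separate the definitions.** A transfusion of this size around surgery would often replace surgical blood loss, which Appendix B also covers. That is fair; anaemia and haemodilution are the clearer cases. Haemodilution is at least plausible here, since cardiovascular eligibility can rest on 20 mL/kg of crystalloid within 6 hours.

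The eCRF guidance might settle the matter, but it is not among the documents and neither document says that it does.

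**Conclusion.** The concern stands as an internal inconsistency of modest severity. The textual conflict is certain: one limb of a primary safety endpoint is worded with and without a bleeding condition. Reporting and stopping of study drug follow one wording, the protocol's between-arm comparison follows the other, and the SAP cites neither.

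The numerical effect is not known. It is zero if reports are filtered to Appendix B before tabulation, or if sites read 7.1 as implying bleeding. If 7.1 events are tabulated unfiltered, both arms' rates rise and the interval widens; on the illustrative inputs the standard error goes from about 1.38 to between 1.54 and 1.80 points around an unchanged 2-point difference. The documents do not support a claim that the planned effect estimate would be biased by equal additions, nor that dilution is bound to occur.

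**What to change.** - Carry one identical definition in Protocol 7.1 and Appendix B, and repeat it in the eCRF guidance.
- Cite that definition in SAP 4.4.6.
- Before unblinding, review reports that qualify only through transfusion and classify them against the definition named in 10.6.4. State this step in the SAP.
- Have the sponsor reconcile the passages that govern discontinuation and SAE reporting (2.7.1, 7.1, 7.2, 7.5) with Appendix B. Which wording governs there is for the sponsor to decide.

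The cost is low: wording in one protocol section, a cross-reference and a sentence in the SAP, an eCRF note, and one blinded listing review. No new data are needed, because Section 7.1 already has each AE recorded with whether it involved bleeding, and blood products entered in the eCRF.
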